### **Standard Research Summary**

### **Purpose of the Study**

Objectives & hypotheses to be tested

The purpose of the study is to evaluate the effects of switching to VLNC cigarettes as a potential strategy for disrupting the pain-smoking reinforcement and withdrawal cycle among smokers with chronic back pain. Adult daily smokers with chronic (> 3 months) non-cancer back pain will be randomly assigned to 4-weeks of Normal Nicotine Content (NNC) or VLNC investigational cigarette use. Participants will attend weekly assessment visits during this time, and will complete EMA assessments during a baseline week of usual brand smoking, and during weeks 1 and 4 of study cigarette use. Participants will also complete assessments of pain and withdrawal following 24 hours abstinence at the start of the study and after 4 weeks of study cigarette use.

Aim 1 will examine effects of NNCs versus VLNCs on smoking and pain over the 4 weeks of study cigarette use and during the 24-hour abstinence tests.

Hypothesis 1a: VLNCs will lead to reductions in nicotine dependence and frequency of smoking over the course of study cigarette use, whereas no change will be observed for NNCs.

*Hypothesis 1b:* Relative to the pre-intervention baseline, smokers assigned to VLNCs will report decreased pain intensity and interference and fewer withdrawal symptoms during the post-treatment 24-hr abstinence test compared with smokers in the NNC condition.

Aim 2 will examine effects of NNCs versus VLNCs on the bidirectional, within-person associations between momentary reports (as assessed with EMA) of smoking urge/behavior, pain and negative affect.

Hypothesis 2a: VLNCs will reduce the magnitude of the within-person associations between momentary reports of pain/negative affect and smoking urge/intent to smoke.

Hypothesis 2b: VLNCs will reduce the magnitude of the within-person association between recent smoking and reports of decreased pain and negative affect.

**Exploratory Aim 3** will examine the effects of NNCs versus VLNCs on changes in smoking and pain-related cognitions, including interest in quitting smoking, abstinence self-efficacy, and smoking to cope with pain.

*Hypothesis:* Following VLNCs, participants will report increased motivation and intention to quit smoking, greater abstinence self-efficacy, and decreased use of smoking as a pain-related coping strategy.

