#### Ecological momentary assessment. Participants will complete EMA

using their smartphone during the 1-week baseline, and during the first and final weeks of study cigarette use. As in our prior research, the MetricWire application platform will be used for acquiring both prompted and smoking-initiated assessments. Prompted assessments: Participants will specify their typically wakeful hours at screening. They will be prompted 5 times daily at random intervals averaging 150 minutes in length. Participants will be asked to indicate how recently they have smoked (1 item), whether this was a study or non-study cigarette (1 item), and whether they are about to smoke (1 item). Participants will then be asked to rate their current urge to smoke (1-item), negative affect (4 to 6 items), positive affect (2 to 4 items), and pain (2 to 4-items; see examples in Table 2). Responses will be on a 9-point scale ranging from "not at all" to "extremely." Participants can delay responding for a brief period of time (e.g., 15 minutes), after which the response will be coded as missing. Smoking-initiated assessments: Participants will be prompted three times each day to indicate the next time they are about to smoke; participants will then respond to a similar set of items as in the prompted assessments before and/or after smoking the cigarette. End of day/Morning assessments: Throughout study cigarette use, participants will be prompted at the end of the day to report how many cigarettes they smoked that day, how many were usual brand versus study cigarettes, and any occasions of non-cigarette tobacco use. Participants will also be asked to rate their severity of withdrawal symptoms over the past 24 hours and the quality of their sleep the night before. If needed, this assessment may be prompted the following morning for participants to report on the prior day. Compensation. Participants will be compensated \$5 per day for completing at least 4 prompted assessments. Participants will earn an additional \$50 per week for completing 4 out of 5 prompted assessments and the end of day/morning assessment every day. This reinforcement schedule is consistent with that used previously in our lab, which has yielded an 88% completion rate.

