#### Compensation:

Participants are compensated for the time and effort they dedicate to the study procedures. They will receive \$30 for the initial screening visit, \$50 for completing the initial abstinence/training session, \$30 for each of the weekly visits, and \$50 for the second abstinence session. In addition, participants can earn a \$100 completion bonus for attending all sessions, up to \$255 for completing EMA, and up to \$600 bonus for biochemical verification of adherence to study cigarettes (\$1235 total). Thus, compensation is provided not only for repeated laboratory visits, but also for use of study cigarettes and completion of EMA. EMA requires multiple responses throughout the day, for a period of 3 weeks, and compensation greatly improves participants' willingness to complete these repeated assessments. In addition, study cigarette use requires committed ongoing effort from participants for a period of several weeks. As such, the compensation is commensurate with the time and effort involved. The \$100 completion incentive is included because high attrition will reduce the statistical power of the study. In addition, the \$600 adherence bonus (or \$200 if participants truthfully disclose non-study cigarette use) is included to maximize compliance with study product because non-study cigarette use will compromise the ability to evaluate group differences. Compensation will be provided at each visit and weekly for EMA. Participants are free to discontinue at any time and will receive compensation for the sessions that they complete at the same rate as participants who complete the study.

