Specific Aim 2 will be to examine the effects of NNCs versus VLNCs on the bidirectional, within-person associations between momentary reports (assessed with EMA) of pain, negative affect, and smoking urge and behavior. Longitudinal associations between smoking/smoking urge and a) pain intensity, b) pain interference, and c) negative affect will be evaluated in separate models. The first set of models will examine each pain measure as a predictor of smoking urge/intent to smoke at each time point. The second set of models will examine recent smoking (i.e., having smoked within the past 15 minutes) as a predictor of each pain measure. Models will include repeated assessments (Level 1) nested within participants (Level 2), nested within weeks (Level 3), with random intercepts. Cigarette condition (NNC or VLNC) and its interaction with week will then be entered to examine the moderating effects of study cigarette use on these within-person associations.

Exploratory Aim 3 will examine the effects of NNCs versus VLNCs on pre- to-post-intervention changes in smoking for pain-related cognitions, assessed at V1 and V5, including smoking to cope with pain, interest in quitting smoking, quit self-efficacy, pain catastrophizing, and pain self-efficacy. For each model, Group will be entered as a between-subjects factor, and Session will be entered as a within-subjects factor.

Sensitivity Analyses will examine the potential impact of a) VLNC compliance (described above) and b) non-opioid analgesic use on the results of primary analyses. Analgesic use will be coded as yes/no at screening and at each weekly visit for the following medication classes: NSAIDS, anticonvulsants, antidepressants, other CNS depressants, muscle relaxants, migraine medications, and corticosteroids. Sensitivity analyses will then examine the impact of weekly use of each medication class as time-varying covariates in primary models.

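### Aim 2 targets within-person associations, but its models do not separate momentary change within a participant from differences between participants

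*Combined protocol and SAP*

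**What the plan says.** The Research Summary lists the momentary associations as the second primary objective. Under Purpose of the Study, Hypothesis 2a reads: "VLNCs will reduce the magnitude of the within-person associations between momentary reports of pain/negative affect and smoking urge/intent to smoke". Hypothesis 2b makes a matching claim about recent smoking and later pain and negative affect.

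Under Data Analysis & Statistical Considerations, Specific Aim 2, the models for Hypothesis 2a are described so: "The first set of models will examine each pain measure as a predictor of smoking urge/intent to smoke at each time point". A second set takes recent smoking as the predictor. The structure is: "Models will include repeated assessments (Level 1) nested within participants (Level 2), nested within weeks (Level 3), with random intercepts". Moderation is described as: "Cigarette condition (NNC or VLNC) and its interaction with week will then be entered to examine the moderating effects".

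The section mentions no centring, no person-mean covariate and no random slope, and it writes out no product of pain with condition and week. It does not say that the rating is entered raw; it is silent on the matter.

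**The concern.** A random intercept does not by itself make a slope a within-person slope. When a time-varying predictor is entered undivided, the coefficient is a precision-weighted average of two quantities. One is how a participant's urge moves when their pain moves. The other is how participants with more pain on average differ from those with less. Hypotheses 2a and 2b concern the first only.

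The same mixing enters the contrast by cigarette condition. Suppose VLNC lowers average urge more in high-pain participants and leaves the moment-to-moment link unchanged. Part of that shift would then be reported as a weaker momentary link. Conversely, if VLNC weakens only the momentary link, the estimate is diluted. In either case a primary objective is answered partly with a different quantity.

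**Working it through.** **The plan's own figures.** The plan gives no figure for this point: no intraclass correlation (ICC) for momentary pain or urge, no rate of intent to smoke and no intercept variance. Its only computed figures are the Aim 1 power values. With the noncentral F for a repeated-measures interaction (N = 48, f = d/2, correlation 0.4), these reproduce: 90.4% and 99.9% for five occasions, and 69.7% and 96.0% for two. They do not bear on Aim 2.

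**Inputs from the documents.** Prompts: "They will be prompted 5 times daily at random intervals averaging 150 minutes in length". Duration: "EMA requires multiple responses throughout the day, for a period of 3 weeks". Completion in earlier work was 88% (Ecological momentary assessment section). Hence 5 × 7 = 35 prompts per week, × 0.88 ≈ 31; over three weeks 105 × 0.88 ≈ 92. So n = 92 reports share an intercept if it is per person. If it is per participant-week, as the written nesting implies, n = 31.

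**Assumed inputs.** Pain ICC (ρx) 0.3–0.7 and urge ICC (ρy) 0.2–0.6. For intent, coded yes/no (a reasonable reading, not stated): event rate p 0.05–0.5 and logit intercept variance τ² 0.25–3.29.

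**Step 1: average slope.** Between-person share = B/(B + W), where

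- W = (n − 1)(1 − ρx)/σ²
- B = [nρx + (1 − ρx)]/(σ² + nτ²)
- urge: σ² = 1 − ρy and τ² = ρy; intent: σ² = 1/[p(1 − p)]

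Worked cases:

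- Urge, n = 92, ρx = 0.5, ρy = 0.4: W = 91 × 0.5/0.6 = 75.8; B = 46.5/37.4 = 1.24; share 1.6%.
- Urge, n = 31, ρx = 0.7, ρy = 0.2: W = 30 × 0.3/0.8 = 11.25; B = 22/7 = 3.14; share 21.8%.
- Intent, n = 31, ρx = 0.7, p = 0.05, τ² = 0.25: σ² = 21.05; W = 9/21.05 = 0.428; B = 22/28.8 = 0.764; share 64.1%.

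| Outcome | n = 92 | n = 31 |
|---|---|---|
| Urge | 0.3–9% | 1–22% |
| Intent (yes/no) | 0.6–53% | 1.8–64% |

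These are ranges over the assumed grid, not bounds. At pain ICC 0.8 the urge share at n = 31 reaches 32%. Simulated random-intercept logistic models (48 people, 40 runs per setting) for part of the intent grid gave shares of 16–44% at n = 31 with τ² of 0.5–1 (7% with τ² = 2), and −2% to 24% at n = 92. With pain split into mean and deviation, the share was −8% to +6%, apart from one noisy setting at 15%.

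**Step 2: the moderation term, which is what Hypothesis 2a tests.** With one intercept per person, the intercept removes a participant's average level but not how that level shifts between weeks. Mean pain × week × condition therefore varies within person and is estimated at report-level precision. Its weight relative to the deviation part is about ρx to 1 − ρx, so the share is close to the pain ICC even for urge.

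Simulation A, for urge: true within-person change −0.2, between-person slope unchanged. Share = 1 − estimate/(−0.2).

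| Intercepts fitted | ρx = 0.3 | 0.5 | 0.7 |
|---|---|---|---|
| Person (no participant-week variance) | −0.138 (31%) | −0.118 (41%) | −0.063 (68%) |
| Person (participant-week variance 0.1, ignored) | −0.141 (30%) | −0.107 (47%) | −0.052 (74%) |
| Person and participant-week | −0.179 (11%) | −0.177 (11%) | −0.120 (40%) |
| Participant-week only | −0.192 (4%) | −0.201 (−1%) | −0.172 (14%) |

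Simulation B, for urge: 48 people, 31 reports per week, urge ICC 0.4, no true within-person change, between-person slope changed by −0.3. With person intercepts the undivided model reported −0.085, −0.132 and −0.199 at ρx = 0.3, 0.5 and 0.7; divided by −0.3, that is 28%, 44% and 66%. A repeat gave −0.08 to −0.21 (27–70%). With modest participant-week variance added it gave −0.02 to −0.11 (7–37%). The centred model gave −0.005 to −0.016, zero within simulation error.

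**Step 3: Hypothesis 2b, average slope.** Assume an ICC for recent smoking of up to 0.3 and a pain ICC of at least 0.5. At n = 92: W = 91 × 0.7/0.5 = 127.4; B = 28.3/46.5 = 0.61; share 0.5%. At n = 31: W = 42; B = 10/16 = 0.625; share 1.5%.

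**The case against.** Several points on the other side stand.

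- **Centring is unspecified; raw entry is not stated.** The plan names a within-person target, and a careful analyst might centre anyway. But the text names the measure itself as predictor and describes no transformation, so following it literally leaves the levels mixed.
- **Every percentage rests on assumed inputs.** Pooling the smoking-initiated reports, for example, gives 8 × 21 × 0.88 ≈ 148 reports per person or about 49 per week, with intent present in roughly 43–50% of them. With pain ICC 0.6–0.75 and τ² = 1, the intent share is then about 4–8% or 11–19%.
- **Mixing alone is not bias.** Bias needs within- and between-person slopes, or their changes, to differ. If the cigarettes had no effect at all, randomisation would make the mixing cancel between arms in expectation. Hypothesis 1a, however, predicts that VLNC changes smoking and dependence, and nothing suggests that such a change would be unrelated to average pain.
- **The nesting may be a slip.** Participants within weeks may be meant as weeks within participants. This does not remove the problem: participant-week intercepts make the average slope worse and the moderation term better, and person intercepts do the reverse.
- **Hypothesis 2b is little affected in its average slope.** This is conceded on the figures above.

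**Conclusion.** The concern holds, mainly for Hypothesis 2a. The plan states a within-person target and specifies models that do not isolate it. Under the assumed inputs, the between-person share of the average slope runs from below 1% to about 22% for urge, and from about 1% to 64% for yes/no intent. In the moderation term, about 25–70% of a between-person change can appear as a false within-person change with one intercept per person. With participant-week intercepts the figure is from near 0 to about 40%, depending on the assumed participant-week variance.

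A reader might infer more than this, and the documents do not support it:

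- that the plan commits to raw ratings (it is silent);
- that intent carries a known contamination of, say, 9–42% (such values lie inside the grid but reflect one choice of inputs);
- that urge is safe because its average-slope share is usually small (the moderation term behaves differently);
- that Hypothesis 2b is equally exposed (its average-slope share is probably small, and its moderation term was not sized).

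**What to change.** In the Specific Aim 2 text:

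1. Enter each momentary predictor as its deviation from the participant's own mean. Choose person mean or person-week mean in advance; the person-week version also removes week-to-week shifts within a participant, so the choice should follow from the association the hypotheses are meant to describe.
2. Add that mean as a separate covariate with its own condition-by-week terms.
3. Write out the deviation × condition × week term, and test Hypothesis 2a on it, with Hypothesis 2b handled the same way for consistency.
4. State whether intercepts are per person, per participant-week or both, and how intent to smoke is coded.

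The cost is a few sentences, a few extra coefficients per model (worth noting with 48 participants) and slightly less precision. No new data are needed. The change should be made before the EMA data are analysed.

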#### **Design & Procedures**

Describe the study, providing details regarding the study intervention (drug, device, physical procedures, manipulation of the subject or the subject's environment, etc.). Discuss justifications for placebo control, discontinuation or delay of standard therapies, and washout periods if applicable. Identify procedures, tests and interventions performed exclusively for research purposes or more frequently than standard of care. Include alternative therapies, concurrent therapies discontinued per protocol, risk benefit ratio, and use of tissue/specimens. Discuss monitoring during washout periods if applicable. Include brief description of follow-up, if any.

**Overview of Study Design.** Participants will complete an initial screening session in which informed consent will be obtained, eligibility is confirmed, and baseline pain and smoking measures are collected. Eligible participants will then be scheduled for a training session/initial abstinence test session. Participants will be asked to abstain from smoking for 24 hours prior to this session. They will complete survey measures, and then will receive training on the EMA procedures and the Metric Wire software will be installed on their smartphone device. Participants will then complete a 1-week baseline period of EMA while smoking their usual brand of cigarettes. Following the baseline period, participants will return for an in-person visit and will be randomly assigned to smoke VLNCs (n=24) or NNCs (n=24) for the next four weeks. Participants will complete 4 weekly lab visits, during which study cigarettes will be supplied and study measures collected. In addition, EMA will continue to be conducted during weeks 1 and 4 of study cigarette use. At the end of study cigarette use, participants will complete a second abstinence challenge session to assess pain and withdrawal following 24 hrs abstinence from smoking. Finally, participants will be contacted by telephone 3 months after completing the study to provide information about quitting behaviors. Details of study sessions are described below and are presented in Table 1.

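### The Aim 2 EMA models allow for no correlation between prompts on the same day; standard errors for H2a may be too small, and for H2b the direction is uncertain

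*Combined protocol and SAP*

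**What the plan says.** The Specific Aim 2 paragraph of Data Analysis & Statistical Considerations gives the dependence structure in one sentence: "Models will include repeated assessments (Level 1) nested within participants (Level 2), nested within weeks (Level 3), with random intercepts". Condition and its interaction with week are then entered as moderators of the within-person associations.

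There are two families of models. For H2a, "The first set of models will examine each pain measure as a predictor of smoking urge/intent to smoke at each time point"; negative affect is handled in the same way. For H2b, the plan uses "recent smoking (i.e., having smoked within the past 15 minutes) as a predictor of each pain measure", and again negative affect is also an outcome.

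The Ecological momentary assessment paragraph under Design & Procedures sets the sampling density. On timing: "They will be prompted 5 times daily at random intervals averaging 150 minutes in length". EMA runs "using their smartphone during the 1-week baseline, and during the first and final weeks of study cigarette use", so there are three EMA weeks. In addition, "Participants will be prompted three times each day to indicate the next time they are about to smoke"; the plan does not say whether these smoking-initiated reports enter the Aim 2 models.

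No section mentions a day level, a serial residual structure, a lagged outcome, a time-of-day term or robust standard errors.

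**The concern.** Random intercepts for person and week remove stable differences in level between people and between weeks. They do not remove carry-over from one prompt to the next, or good and bad days within a week. Given person and week, the model as written treats two ratings 150 minutes apart as no more alike than two ratings six days apart.

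If the predictor and the residual both persist within the day, each prompt carries less information about the slope than the model assumes, and the standard error of the slope comes out too small. This is separate from whether slopes vary between people: every calculation below gives all participants the same slope.

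Aim 2 is one of the two primary objectives. A falsely significant moderation could be read as VLNCs weakening the link between pain and smoking, and the background section presents this work as groundwork for a large trial. The sample size section claims ample power for Aim 2 partly because EMA adds repeated assessments. That argument depends on how much independent information each prompt carries, which the plan does not address.

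**Working it through.** **The plan's own figures.** There is no numerical power or precision figure for Aim 2. The Aim 1 figures reproduce with f = d/2, λ = f²·N·m/(1 − r), and df = m − 1 and (N − 2)(m − 1), taking N = 48 and r = 0.4:
- Five occasions: λ = 0.2²·48·5/0.6 = 16 and 0.3²·48·5/0.6 = 36, giving 90.4% and 99.9% (stated 90% to 99%).
- Two occasions: λ = 6.4 and 14.4, giving 69.7% and 96.0% (stated 70% to 96%).

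These concern visit-level data and say nothing about correlation between prompts.

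**Inputs from the documents.** Participants: 24 + 24 = 48 ("will be randomly assigned to smoke VLNCs (n=24) or NNCs (n=24) for the next four weeks"). Prompts: 5 a day × 7 days × 3 weeks = 105 per person. Completion: the plan cites an earlier schedule "which has yielded an 88% completion rate".

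**Assumed.** The within-day lag-one correlations of the predictor (ρx) and the residual (ρe), and any day-level variance share. The documents give none of these, so a range is shown.

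**Closed form.** For a within-person slope with five prompts a day, first-order autoregression within the day and independent days, the ratio of true to model variance is

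VIF = 1 + 2·Σ(k = 1 to 4) (1 − k/5)·(ρx·ρe)^k.

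At 0.5 and 0.5, ρx·ρe = 0.25, so VIF = 1 + 2·(0.2 + 0.0375 + 0.00625 + 0.00078) = 1.489. The SE ratio is √1.489 = 1.22.

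| ρx = ρe | VIF | True SE / model SE | Coverage of nominal 95% CI | Two-sided type I error |
|---|---|---|---|---|
| 0.2 | 1.066 | 1.03 | 94.2% | 5.8% |
| 0.3 | 1.154 | 1.07 | 93.2% | 6.8% |
| 0.4 | 1.290 | 1.14 | 91.6% | 8.4% |
| 0.5 | 1.489 | 1.22 | 89.2% | 10.8% |

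If ρx = 0, every term in the sum vanishes: VIF = 1 and coverage is 95% whatever ρe is. Residual autocorrelation alone does no harm here.

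The closed form assumes that every prompt is answered. With 88% completed at random, the excess shrinks by that factor: at 0.5, 1 + 0.88·0.489 = 1.430, a ratio of 1.20.

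**Simulation, H2a type.** 1,500 runs per setting, 88% completion, a common slope, and as the contrast the arm difference in slope change from baseline week to study week 4:
- 0.3/0.3: ratio 1.05, coverage 94.2%.
- 0.4/0.4: ratio 1.14, coverage 91.9%.
- 0.5/0.5: ratio 1.18, coverage 91.1%.
- ρx = 0, ρe = 0.5: ratio 0.98, coverage 95.5%.
- Day effects alone (20% of variance in predictor and in residual): ratio 1.08, coverage 92.8%.
- The same day effects plus 0.3/0.3: ratio 1.18, coverage 89.1%.

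The Monte Carlo error of a ratio is about 1/√(2·1500) = 0.018.

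**Fitted three-level random-intercept model.** At 0.5/0.5 (500 runs) the empirical SE is 0.0914 against a model SE of 0.0750: ratio 1.22, coverage 88.6%. At ρx = 0, ρe = 0.5 (150 runs) coverage is 96%, so there is no shortfall.

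**Simulation, H2b type.** Binary predictor, ρe = 0.5, correlation on the latent scale of the predictor:

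| Latent ρx | True SE / model SE | Coverage |
|---|---|---|
| −0.3 | 0.95 | 95.9% |
| 0 | 0.98 | 95.1% |
| 0.3 | 1.06 | 93.9% |
| 0.5 | 1.08 | 92.7% |

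**Remedy checked.** With participant-clustered standard errors and t on 48 − 2 = 46 df, coverage was 94.3% to 95.7% in all 16 simulated settings. At 0.5/0.5 the clustered SE was 0.089 against a true 0.088, with coverage 95.4%.

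**The case against.** A reader might infer that the intervals for both H2a and H2b are too narrow and that every Aim 2 test exceeds 5%. The documents do not support that. The shortfall needs positive correlation in the predictor as well as the residual. The H2b predictor records smoking in the last 15 minutes, sampled about 150 minutes apart. Nothing in the plan says that it persists from prompt to prompt; it could be unrelated or even negatively related. This objection stands in full for H2b.

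For H2a, the correlations are assumptions. At 0.2 the effect is negligible, so the honest range starts near zero. The inflation is also two-sided: at 0.5, the false-positive rate in the direction of VLNCs weakening the association is about 10.8%/2 = 5.4%, against a nominal 2.5%. Both points stand and limit the size, not the mechanism.

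The plan never says that residuals are independent, and generalized mixed models do not exclude a structured residual. That is true, but the Aim 2 paragraph names only random intercepts, and conditional independence is what that model gives when fitted as written.

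Finally, a Gaussian autoregressive residual does not carry over directly to intent to smoke, which is probably a yes/no item. This also stands, and is why the fix leads with clustered standard errors.

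**Conclusion.** The point holds in conditional form. For H2a, the specified model gives standard errors that are too small if predictor and residual are both positively correlated within day. That is plausible for pain and affect ratings taken a few hours apart. On the closed form, the true SE is 3% to 22% larger than the model SE for correlations of 0.2 to 0.5, with type I error of about 6% to 11%. It is about 18% larger in simulation with a 20% day-level variance share plus correlation of 0.3. There is no shortfall if the predictor is uncorrelated.

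For H2b, neither size nor direction can be fixed from the documents. Pooling smoking-initiated reports with random prompts could strengthen the dependence, but the plan does not say whether this is intended.

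The plan's nesting order puts participants within weeks. It was read here as weeks within participants; the order needs correcting but does not alter this finding.

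**What to change.** In the Specific Aim 2 paragraph, specify participant-clustered standard errors with a small-sample correction (t on about 46 df) for all Aim 2 models, H2a and H2b alike, including the intent-to-smoke model. The coverage check above used a continuous outcome, so it is not direct evidence for a binary one.

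For the continuous outcomes (urge, pain, negative affect), also add a random intercept for day within participant and a continuous-time first-order autoregressive residual based on actual minutes between prompts, at least as a sensitivity analysis. State whether smoking-initiated reports enter these models.

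The cost is a few sentences of analysis plan, slightly more analysis work, and somewhat wider confidence intervals where the dependence is real. Where the predictor is uncorrelated almost nothing is lost: at ρx = 0, ρe = 0.5, coverage was 95.5% as written and 95.7% clustered. Fixing the error structure before analysis also prevents it from being chosen after the results are seen.

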# Research Summary

#### State your primary study objectives

- 1. To examine the effects of NNCs versus VLNCs on smoking and pain over 4 weeks of study cigarette use and following a 24-hour abstinence challenge.
- 2. To examine the effects of NNCs versus VLNCs on the bidirectional, within-person associations between momentary reports (as assessed with EMA) of smoking urge/behavior, pain, and negative affect.

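### Aim 2 asks whether cigarette condition changes within-person slopes, but the terms named do not contain the momentary predictor, and the random effects named are too thin for the slope term a reader would infer

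*Combined protocol and SAP*

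**What the plan says.** The second primary objective is "To examine the effects of NNCs versus VLNCs on the bidirectional, within-person associations between momentary reports". Under Purpose of the Study, Hypothesis 2a is that "VLNCs will reduce the magnitude of the within-person associations between momentary reports of pain/negative affect and smoking urge/intent to smoke", and Hypothesis 2b that "VLNCs will reduce the magnitude of the within-person association between recent smoking and reports of decreased pain and negative affect". Both are statements about slopes.

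The model is in Data Analysis & Statistical Considerations, Specific Aim 2. For the first direction, "The first set of models will examine each pain measure as a predictor of smoking urge/intent to smoke at each time point"; for the second, recent smoking predicts each pain measure. Assessments are "nested within participants (Level 2), nested within weeks (Level 3), with random intercepts". The treatment terms follow: cigarette condition "and its interaction with week will then be entered to examine the moderating effects of study cigarette use on these within-person associations".

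The section does not name a product of the momentary predictor with condition, a centring rule, a random slope or a deciding contrast for Aim 2. The sample size paragraph gives no Aim 2 calculation. It expects ample power for Aim 2 on the strength of the Aims 1 and 3 estimates and the number of EMA reports. For its Aim 1 power it points to a section called Statistical Design and Power, which is not in the document reviewed.

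**The concern.** A treatment effect on a slope is carried by a product that includes the predictor. Condition and condition × week describe how the average outcome differs by arm and week. The same section uses this form, Group × Week, in Aim 1 to test changes in level; it cannot also test changes in slope.

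An analyst who sees the intent will add a product term, but must then choose between a two-way and a three-way product, how to centre the predictor, and which weeks to compare. If random intercepts are the only random effects, the model treats slope differences between person-weeks as independent report-level noise. The slope term then looks more precise than it is. At stake is whether a primary objective is tested at all and, if so, at its nominal error rate.

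**Working it through.** **1. The plan's own figures.** They concern Aim 1 only. With f = d/2, λ = f²·N·m/(1 − r), df1 = m − 1 and df2 = (N − 2)(m − 1):

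- d = 0.4, N = 48, r = 0.4, m = 5: λ = 0.04 × 48 × 5/0.6 = 16; power 90.4% (stated 90%).
- Same with m = 2: λ = 6.4; power 69.7% (stated 70%).
- d = 0.6, r = 0.4: 99.9% and 96.0% (stated 99% and 96%).
- r = 0.5, m = 2: 77.4% and 98.3% (stated 77% and 98%).
- N = 32, d = 0.5, r = 0.5: 95.7% and 78.1% (stated 96% and 78%).

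All reproduce. All are for group × session effects on a mean, so none speaks to a slope.

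**2. Inputs for Aim 2.** From the documents: 24 per arm; three EMA weeks; 5 prompts × 7 days × 88% completion = 30.8, taken as n = 31 reports per person-week. Assumed, because the documents give no values: residual SD 1, within-person predictor SD 1, slope SD between people τp, and slope SD between person-weeks τw.

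**3. The literal terms.** With a centred predictor, changing the slope by δ changes the expected mean outcome by δ × 0 = 0, so condition × week cannot see it. In simulation (at least 2,000 trials; τp = 0.2, τw = 0.1, slope lowered by 0.2 in the VLNC arm) condition × week rejected in 4.0% of trials. A test of slope change on the same data rejected in 60%.

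That simulation did not use the level order as written, which puts participants inside weeks and so shares no intercept across a participant's weeks. Assume person intercept SD 1 and person-week intercept SD 0.4. The true variance of a participant's week-to-week difference is 2 × (0.16 + 1/31) = 0.385; the model would assume 2 × (1 + 0.16 + 1/31) = 2.385. True SE / model SE = √(0.385/2.385) = 0.40, and the literal test would reject almost never. Either way it does not test Hypotheses 2a or 2b.

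**4. The inferred three-way term** (week 4 versus baseline, random intercepts, no random slopes).

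- True variance: (4/24) × (1/n + τw²).
- Variance the model reports: (4/24) × (1 + τp² + τw²)/n.
- Ratio of true SE to model SE: √[(1 + n·τw²)/(1 + τp² + τw²)].
- Null rejection: 2 × [1 − Φ(1.96/ratio)].

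| τp | τw | SE ratio | Null rejection, formula | Null rejection, simulated |
|---|---|---|---|---|
| 0.2 | 0 | 0.98 | 4.6% | 5.3% |
| 0.2 | 0.10 | 1.12 | 7.9% | 8.6% |
| 0.2 | 0.15 | 1.26 | 12.1% | 12.7% |
| 0.2 | 0.20 | 1.44 | 17.4% | 18.0% |
| 0.2 | 0.30 | 1.83 | 28.5% | 27.3% |
| 0.3 | 0.30 | 1.79 | 27.4% | 30.2% |

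Example, third row: (1 + 31 × 0.0225)/(1 + 0.04 + 0.0225) = 1.6975/1.0625 = 1.598; the square root is 1.26. Fitted mixed models with a participant intercept gave 18.6% at τp = τw = 0.2 (488 fits) and 5.9% at τp = 0.2, τw = 0 (492 fits). With slopes allowed to vary, the null rate was 4.6% to 5.5%.

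**5. What the inflation depends on.** If slopes differ only between people and predictor variance is equal, person slopes nearly cancel in the three-way contrast (simulated 5.3% to 6.8%). If the predictor's person-week SD itself varies (assumed log-SD 0.3 or 0.5), constant person slopes with τp = 0.1 to 0.3 give 6% to 17% or 9% to 32%. A predictor × condition term pooled over weeks 1 and 4 has ratio √[(1 + 2n·τp² + n·τw²)/(1 + τp² + τw²)]. At τw = 0 this gives 12%, 28% and 43% for τp = 0.1, 0.2 and 0.3.

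**6. Other outcomes.** One-contrast null rates for a binary intent outcome at about 30% prevalence were 7.0% (τw = 0.15) and 11.8% (τw = 0.30). For Hypothesis 2b they were 10.9% to 11.2% (τw = 0.30).

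**7. Power with valid standard errors** (participant-clustered, τp = 0.2, 31 reports, τw = 0 / 0.15 / 0.30): 69 / 46 / 26% for a slope change of 0.2, and 100 / 97 / 74% for 0.4.

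**The case against.** The purpose clause says that the terms are there to examine moderation of within-person associations, so a competent analyst would include the predictor in the product. That stands: intent is not in doubt, and a reader who infers that Aim 2 is misconceived, or that its data cannot answer the question, goes beyond the documents. Intent still leaves the product, the centring and the contrast open.

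The plan says random intercepts; it does not exclude random slopes. That also stands, and the second half of the point is conditional on fitting only what is named.

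A reader might infer that the standard error is too small whenever slopes vary. The calculation does not support this: variation between people alone, with equal predictor variance, leaves the three-way term near nominal. Nor are the larger rates evidence about this trial. The documents give no slope SDs, and 0.30 between person-weeks against 0.2 between people would mean that only 0.04/(0.04 + 0.09) = 31% of slope variance is stable over time.

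A reader might also infer that the binary intent outcome has no suitable model. The section specifies generalized mixed models, which allow for it; only the link is unnamed. Choosing week 4 as the deciding week is a preference, since the hypotheses name no week and a joint test over weeks is compatible with the text.

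Finally, the Statistical Design and Power section might name the term. It was not available, so this cannot be ruled out.

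**Conclusion.** The concern holds as a specification and model gap in a primary objective; it is not a design flaw and should be fixed. Confidence is high that the slope term is not named in the text reviewed, and that the named terms have essentially no power for Hypotheses 2a and 2b when the predictor is centred. That needs no assumption about slope SDs.

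Confidence is also high in the direction of the standard-error problem, given slopes that vary between person-weeks or unequal predictor variance. Its size, about 9% to 30% null rejection in the Gaussian case for τw of 0.10 to 0.30, is an illustration. It approaches nominal as τw falls to zero with equal predictor variance.

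A reader might conclude that Aim 2 is underpowered. The documents do not support that either: illustrative power runs from 26% to 100% over the assumed slope changes and SDs. They support only that the expectation of ample power has not been checked against the term that would be tested.

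**What to change.** In the Specific Aim 2 text:

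- Name predictor × condition × week, with all lower-order terms, as the test of Hypotheses 2a and 2b.
- Use the person-mean-centred predictor and enter the person mean as a separate term.
- Add random slopes by participant and participant-week, or use standard errors clustered on participant with a small-sample correction.
- Correct the level order to assessments within participant-weeks within participants, since each participant contributes to all three EMA weeks.
- Prespecify the deciding contrast: either the joint test over weeks or baseline to week 4. Name the link for the intent outcome.
- Report condition × week separately, as an effect on level.

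In the sample size paragraph, check the Aim 2 power statement against the named term, or soften it. If the Statistical Design and Power section already names the term, carry it into the Aim 2 text.

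The cost is analysis work, a more complex model and a wider standard error; no new data are needed. For a slope change of 0.2 with τw = 0.15 and 31 reports, rejection falls from 68% with random intercepts only, where the null rate is 12.7%, to 46% with clustered standard errors.
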